9.4. Adverse events that do not require reporting

All Adverse Events will be recorded by the research staff. These can be extracted from the CSAM MedSciNet database as a list of events with onset and end dates.

9.5. Premature Termination of the Trial

The trial may be prematurely discontinued by the Sponsor, Chief Investigator or Regulatory Authority based on new safety information or for other reasons given by the Data Monitoring & Ethics Committee/ Regulatory Authority or ethics committee concerned.

If the trial is prematurely discontinued, active participants will be informed and no further participant data will be collected. The Competent Authority and Research Ethics Committee will be informed within 15 days of the early termination of the trial.

10. Statistics

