4.2. Primary endpoints

1. Total VZV specific cell mediated geometric mean titer (GMT) ratios change from baseline to week 12 (4 weeks after second vaccine dose).

2.Total VZV specific antibody geometric mean titer (GMT) ratios change from baseline to week 12 (4 weeks after second vaccine dose).

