6.7. Withdrawal of Participants

Participants have the right to withdraw from the study at any time for any reason. The investigator also has the right to withdraw participants from the study drug in the event of inter-current illness, AEs, SAEs, SUSARs, protocol violations, cure, administrative reasons or other reasons. It is understood by all concerned that an excessive rate of withdrawals can render the study un-interpretable; therefore, unnecessary withdrawal of participants should be avoided. Should a participant decide to withdraw from the study, all efforts will be made to report the reason for withdrawal as thoroughly as possible. Should a participant withdraw from study vaccination only, efforts will be made to continue to obtain follow-up data, with the permission of the participant. Any samples and/or data already obtained prior to withdrawal will be used in the analysis.

Participants who wish to withdraw from study vaccination will be asked to confirm whether they are still willing to attend for the subsequent study visits.

To ensure trial endpoints are met, 62 participants will need to have received both injections. The sample size calculations therefore allow for up to 70 participants to be recruited to ensure this occurs. Participants who withdraw prior to their second injection will therefore be replaced up to an including when 62 participants have received 2 vaccinations.

In all cases the date and reasons for withdrawal or withholding the dose of medication will be clearly stated on the participant's CRF. If the reason for removal of a participant from the trial is an adverse event or an abnormal laboratory test result, the principal specific event or test will be recorded on the CRF.

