Refer to the Table 1, for the visit schedule. Note that unscheduled visits may be required. Immediate safety concerns should be addressed by the PI as soon as he or she becomes aware of the concern to determine if the participant should continue or discontinue study vaccination. The PI will inform the Sponsor immediately upon occurrence or awareness. Adherence to the study design requirements, including those specified in the visit schedule, is essential and required for study conduct. All participants will be enrolled and followed up for 48 weeks. The vaccination phase will last 8 approximately weeks.

Procedures prior to study participation

Potential participants will be identified through HIV clinics. Eligible individuals will be informed about the trial and given a patient information sheet at least one day prior to consent is taken which explains the aims, methods, and potential benefits and hazards of the trial.

Screening visit

The study staff conducting the Screening visit will:

- Introduce themselves and their role to the participant and confirm the identity of the participant.
- Confirm that the means of contact is adequate to conduct the contact/visit

• Participants will be provided with the study information, including the participant information sheet (PIS) to read. They will discuss the study with a member of the research team in person or remotely. Consent will be obtained by an investigator.

After informed consent has been collected, a unique trial identifier will be assigned by the study staff. The screening visit will conduct:

- Eligibility assessment (as per inclusion/exclusion criteria)
- Demographics recording
- Medical History
- Vital signs
- Temperature

- Full physical exam
- Urine pregnancy test (women of childbearing potential only)
- Concomitant medications review
- Adverse Events Review

Procedures prior to the first vaccination at enrolment visit

Screening and enrolment can occur on the same day. If not, the enrolment visit should take place within 8 weeks following the screening visit. If more than 8 weeks have elapsed study repeat the screening assessments.

Study staff will review information related to eligibility collected at screening and determine whether there are any clinically relevant abnormalities that require further investigation prior to enrolment.

Baseline, Week 0 (+8 weeks)

The baseline visit will conduct:

- Eligibility Assessment (as per inclusion/exclusion criteria)
- Vital signs
- Temperature

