†Gastrointestinal symptoms include nausea, vomiting, diarrhoea and/or abdominal pain. Please record each symptom as a separate adverse event.

Clinical laboratory parameters and other abnormal assessments qualifying as adverse events or serious adverse events

Abnormal laboratory findings (e.g. clinical chemistry, haematology, urinalysis) or other abnormal assessments that come to the attention of, and are judged by, the

investigator to be clinically significant will be recorded as AEs or SAEs if they meet the definition of an AE.

Reporting Responsibilities

Guy's and St Thomas' NHS Foundation Trust has delegated the delivery of the Sponsor's responsibility for Pharmacovigilance (as defined in Regulation 5 of the Medicines for Human Use (Clinical Trials) Regulations 2004 to the King's Health Partners Clinical Trials Office (KHP-CTO).

Symptoms, adverse events and reactions will be recorded by the research study team. All SAEs, pIMDs SARs and SUSARs (except those specified in this protocol as not requiring reporting) will be reported immediately (and certainly no later than 24hrs) by the Investigator to the KHP-CTO and CI for review in accordance with the current Pharmacovigilance Policy. Guidance for SAE reporting can be found at: https://khpcto.co.uk/SAEs/SAE_Reporting.php.

The SmPC with current regulatory approval for the trial will be used by the Investigator (or delegate) to assess SAE reports to identify SUSARs.

The KHP-CTO will maintain an SAE tracking database of all events reported. The KHP-CTO will report SUSARs to the regulatory authorities (MHRA, competent authorities of other EEA (European Economic Area) states) in which the trial is taking place.

The Chief Investigator will report to the relevant ethics committee. Reporting timelines are as follows:

- SUSARs which are fatal or life-threatening must be reported not later than 7 days after the sponsor is first aware of the reaction. Any additional relevant information must be reported within a further 8 days
- SUSARs that are not fatal or life-threatening must be reported within 15 days of the sponsor first becoming aware of the reaction.

The Chief Investigator and KHP-CTO (on behalf of the sponsor), will submit a Development Safety Update Report (DSUR) relating to this trial IMP, to the MHRA and REC annually.

Causality

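### Section 9.5 ends all participant data collection after an early stop, even one for safety, and cannot be squared with the safety-reporting duties in section 9.2

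*Protocol*

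**What the plan says.** Protocol section 9.5 gives the grounds for an early stop: "The trial may be prematurely discontinued by the Sponsor, Chief Investigator or Regulatory Authority based on new safety information", or other reasons from the oversight bodies it names. Its next paragraph sets the consequence: "If the trial is prematurely discontinued, active participants will be informed and no further participant data will be collected". No exception is made for safety data or for a stop made on safety grounds.

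Section 9.2 sets the reporting duties: "All SAEs, pIMDs SARs and SUSARs (except those specified in this protocol as not requiring reporting) will be reported immediately", with 24 hours as the outer limit. A fatal or life-threatening SUSAR goes to the authorities within 7 days, and additional relevant information within a further 8 days. Unplanned pregnancies also go through the SAE reporting system.

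Section 6.7 covers the individual case: "Should a participant withdraw from study vaccination only, efforts will be made to continue to obtain follow-up data, with the permission of the participant". For withdrawal it adds: "Any samples and/or data already obtained prior to withdrawal will be used in the analysis".

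Section 7.1 sets the planned duration: "All participants will be enrolled and followed up for 48 weeks". Table 1 and section 7.1 schedule a review of adverse events and immune-mediated disease at every visit to week 48.

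Sections 11 and 12 provide for neither a steering committee nor an independent data monitoring committee. Section 11 gives safety oversight to the Trial Management Group.

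**The concern.** Section 9.5 is a stated rule, not a detail left for later. A statistical analysis plan could not repair it, because no analysis can recover data that the protocol says not to collect.

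Safety is a secondary objective (section 4.1), and events of Grade 3 or higher are a secondary endpoint (section 4.3). A stop on safety grounds is the situation in which later events among people already exposed are of most interest. Under 9.5 as worded, it is also the situation in which recording ceases. The Trial Management Group cannot review events that nobody records.

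**Working it through.** The point concerns a rule and has no figure in the plan to reproduce, so the check sets the provisions side by side.

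**1. Does 9.5 carry an exception?** No. The ban on further data applies to every early termination, including one for new safety information. No other section provides for safety follow-up after a trial-level stop.

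**2. 9.5 against 9.2.** An investigator can report an SAE, a pIMD or a pregnancy only by collecting information on a participant.
- Suppose a vaccinated participant has an SAE the week after the stop. Section 9.2 calls for a report within 24 hours; section 9.5 says that no participant data are collected.
- Suppose a fatal or life-threatening SUSAR itself leads to the stop. The first report is due by day 7 after the sponsor becomes aware, and further information within 8 more days, so as late as day 7 + 8 = 15. If the trial is stopped within that time, 9.5 read literally bars gathering the information that 9.2 requires.
- Section 5.3 asks for contraception until 2 months after dose two. A stop inside that time would end the capture of pregnancies that 9.2 sends through the SAE system.

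Both instructions cannot be followed as written.

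**3. 9.5 against 6.7.** The events differ: one person stopping vaccination in a running trial, against closure of the trial. The rules can coexist, but they pull in opposite directions. One person who stops vaccination is followed with permission; a whole cohort halted on a safety signal is not.

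**4. 9.5 against the 48-week follow-up.** The 48 weeks describe the conduct of a running trial, and any early stop shortens them. This is not a contradiction. The scheduled reviews do show that the protocol regards events up to week 48 as worth recording.

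**5. Scale, for illustration only.** Inputs: 70 participants (section 4.5) and 48 weeks (section 7.1). Assumption: all 70 are enrolled and dosed when the stop comes.
- Planned follow-up: 70 × 48/52 = 64.6 person-years.
- Share unrecorded after a stop at mean follow-up of f weeks: 1 − f/48.

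| Mean follow-up at stop (weeks) | Share unrecorded | Person-years unrecorded |
|---|---|---|
| 12 | 75% | 48.5 |
| 24 | 50% | 32.3 |
| 36 | 25% | 16.2 |

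The stop times are assumed. The table shows what the rule would forgo at each one, not how likely a stop is.

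**The case against.** The best defence is that 9.5 closes a trial and does not say that the duties in 9.2 lapse. Section 9.2 ties pharmacovigilance to the clinical trials regulations, provides an SAE tracking database and annual safety reports, and would probably be honoured in practice. This is a low-risk trial of a licensed vaccine with no interim analysis, so an early stop may well never happen. All of this stands and limits the weight of the point. It does not remove the clash: sites are told both to report events and to collect no data, and the protocol does not say which instruction prevails.

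Several stronger readings are tempting, and the documents do not support them.

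- *That 9.5 contradicts 6.7 and the 48-week follow-up.* The scopes differ, as shown in the working.
- *That nothing offsets the rule because there is no independent committee.* Section 11 assigns safety oversight to the Trial Management Group.
- *That the trial could not describe the event that stopped it.* An event within the trial would come before the stop and fall under the 24-hour rule. What is at risk is its further course and later events in others. The new safety information might also come from outside the trial.
- *That pending week-12 samples are lost.* Section 9.5 does not say that blood already drawn is discarded, and 6.7 keeps samples taken before an individual withdrawal. Only undrawn samples would be forgone, and whether to continue research bleeds after closure is a debatable design choice.
- *That pIMDs typically appear late.* The protocol gives no latency for them, so the argument cannot rest on it.

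**Conclusion.** The point holds for safety data. Section 9.5, read literally, ends the recording of later AEs, SAEs, pIMDs and pregnancies in participants already vaccinated, and it conflicts with the reporting duties in 9.2. Against 6.7 it is an inconsistency of principle only.

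Up to 70 people could be affected. The number of events that would go unrecorded cannot be derived from the protocol, because it depends on whether and when a stop occurs. If the trial runs to completion the effect is nil: neither the primary nor the secondary analyses change. The conclusion rests on reading 9.5 as written and on the absence of any other provision for follow-up after a stop. The correction is worth making beforehand, since unrecorded follow-up cannot be reliably recovered later.

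**What to change.** Reword 9.5 so that early termination ends enrolment and research procedures, while AEs, SAEs, pIMDs and pregnancies continue to be collected and reported, with consent, for participants already dosed. State how long this lasts, either as a defined period or up to a closing contact. Cross-refer to 9.2 so that the reporting duties, including additional SUSAR information, plainly survive a stop, and bring the wording into line with 6.7. The same edit can resolve the mention in 9.5 of a Data Monitoring & Ethics Committee, since section 12 says that an independent data monitoring committee is not required.

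The change concerns data collection only and leaves doses, schedule and grounds for stopping as they are. It costs a sentence or two, plus some safety follow-up work by sites if a stop occurs.

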10.1. Sample Size

The two study groups (PLWH aged \geq 50 years, and young adults with perinatally acquired HIV infection) will be considered and analysed separately. Therefore, the sample size described below will be obtained in each patient population.

This is a single arm study which aims to precisely estimate the average change at 12 weeks in (i) VZV specific antibody and (ii) T cell responses. The precision of the population estimates will be quantified using 95% confidence intervals (CI). Therefore, the sample size calculations are performed to ensure the width of the CIs are sufficiently narrow. The acceptable level of precision was derived using clinical judgment of a meaningful change, alongside practical considerations on participant recruitment numbers.

Due to their anticipated log-normal distribution, the primary study endpoints will both be summarised using geometric means. As this is equivalent to calculating the [arithmetic] mean of the natural logathithm titer values (followed by backtransformation to the original scale), calculations are presented here on the natural logarithm scale. Note that the results will be presented in study reports after backtransformation to the original scale:

1. Total VZV specific cell mediated geometric mean titer (GMT) ratios change from baseline to week 12 (4 weeks after second vaccine dose)

A previous study by Benson et al of the Zostavax vaccine reported a geometric mean fold-change at 12 weeks of 3.8. This corresponds to an absolute change on the natural log scale of 1.33. The corresponding standard deviation was also derived from this study and conservatively rounded up to 3.4. A confidence interval width of 3 $\log_e 5x10^5$ cells was chosen as an acceptable level of precision. The probability was set at 90% (analogous to a study power: there is a 90% chance that the CI will be no wider than 0.6 in a future study). Based on these assumptions, we will have 90% probability of estimating the mean to a precision of 3 (the 95% confidence interval will have a width of ±1.5) with a sample size of 30 individuals (Stata, Version 16: command used ciwidth onemean, w(3) probwidth(0.9) sd(3.4)).

2.Total VZV specific antibody geometric mean titer (GMT) ratios change from baseline to week 12 (4 weeks after second vaccine dose)

Benson et al reported a geometric mean fold-change at 12 weeks of 1.80. This corresponds to an absolute change on the natural log scale of 0.59. The corresponding standard deviation was derived from this study and conservatively rounded up to 0.7. A confidence interval width of 0.6 log_e $5x10^5$ cells was chosen as an acceptable level of precision. Based on these assumptions, we will have 90% probability of estimating the mean to a precision of 0.6 with a sample size of 31 individuals (Stata, Version 16: command used ciwidth onemean, w(0.6) probwidth(0.9) sd(0.7)).

To end up with 61 evaluable participants, we will recruit 70 individuals: approximately 35 in each group.

We acknowledge only common adverse events will be identified in this study, due to the relatively small study sample size. However, other studies of this licenced vaccine have studied safety in great detail.

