Primary objective	To assess the cell-mediated and humoral immunity profile of the Shingrix vaccine in HIV positive adults aged 50 years and over, and those with perinatally acquired HIV infection and are aged 18 and over.
Secondary objectives	 Detailed characterization of cell-mediated and humoral responses to the candidate vaccine
	2. To assess the impact of current CD4, nadir CD4, CD4: CD8 on immunogenicity
	 To assess the impact of vaccination on HIV reservoirs
	 To explore BCR and TCR repertoires in response to vaccination.
	 To investigate the sequences of viruses from individuals who develop shingles after vaccination.

	 To assess the safety of the Shingrix vaccine in HIV positive adults aged 50 years and over, and those with perinatally acquired HIV infection aged 18 and over.
Trial design	Open, single arm intervention study
Endpoints	Primary endpoints
	1. Total VZV specific cell mediated geometric mean titer (GMT) ratios change from baseline to week 12 (4 weeks after second vaccine dose)
	2.Total VZV specific antibody geometric mean titer (GMT) ratios change from baseline to week 12 (4 weeks after second vaccine dose)
	Secondary endpoints
	 Change of VZV specific cell mediated mediated geometric mean titer (GMT) ratios change from baseline to week 48 Change of VZV specific antibody mediated geometric mean titer (GMT) ratios change from baseline to week 48 Occurrence of adverse events of Grade 3 or higher severity Viral sequence of shingles infections
Sample size	70 (61 evaluable)
Summary of main eligibility criteria (see sections 5.1/5.2 of protocol for	Inclusion criteria: 1. HIV positive ≥50 years OR 2. Perinatally acquired HIV-positive individuals who are aged 18 and over
iuny engibility criteria)	Exclusion criteria: 1. Received shingles vaccine in past 12 months

	 Active herpes zoster disease in past 6 months preceding the first dose of study vaccine Pregnant or unwilling to use contraception
IMP, dosage and route of administration	Vaccination schedule: week 0, week 8
Active comparator product	nil
Maximum duration of treatment of a participant	2 months
Version and date of protocol amendments	

2. Glossary of Terms

AE	Adverse Event
AR	Adverse Reaction
BCR	B cell receptor
CA	Competent Authority
CI	Chief Investigator
CRF	Case Report Form
CRO	Contract Research Organisation
СТА	Clinical Trial Authorisation
CTIMP	Clinical Trial of Investigational Medicinal Product
CTU	Clinical Trials Unit
	Data Monitoring Committee

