6.3. Selection of Participants

Participants will be recruited from HIV clinical centres which jointly provide medical care for over 10,000 PLWH: and combined have one of the largest European cohort of individuals with perinatally acquired HIV infection.

We will recruit up to 70 HIV positive adults with the aim for n=31 \geq 50 years old and n=31 adults with perinatally acquired HIV over the age of 18 years who have completed the study.

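### The evaluable target of 61 cannot hold two groups of 31, and the replacement rule counts pooled second injections, not week-12 pairs per group

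*Protocol*

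**What the plan says.** All references are to the protocol.

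- Section 10.1 treats people aged 50 or over and adults with perinatally acquired HIV as separate analyses: "Therefore, the sample size described below will be obtained in each patient population".
- The same section derives 30 for the cell-mediated endpoint. For the antibody endpoint it concludes: "we will have 90% probability of estimating the mean to a precision of 0.6 with a sample size of 31 individuals".
- It closes the calculation with "To end up with 61 evaluable participants, we will recruit 70 individuals: approximately 35 in each group". The sample size row of the synopsis also gives 70 with 61 evaluable.
- Section 6.3 aims for 31 people aged 50 or over and "n=31 adults with perinatally acquired HIV over the age of 18 years who have completed the study", which makes 62 completers.
- Section 6.7 requires 62 participants with both injections and sets the replacement rule: "Participants who withdraw prior to their second injection will therefore be replaced up to an including when 62 participants have received 2 vaccinations".
- Section 4.2 defines both primary endpoints as the change from baseline to week 12, four weeks after the second dose. Section 6.4 omits participants who co-enrol in a conflicting study from the primary immune analysis.

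**The concern.** The design has no hypothesis test. Its only quantitative promise is a 90% probability, in each group and for each endpoint, that the 95% confidence interval is no wider than a stated value. The number of analysable pairs per group decides whether that promise is kept.

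The target is given as two different totals (61 and 62) and is counted on three different events: being evaluable, receiving both injections, and completing the study. The only count that drives recruitment is the one in section 6.7. It is taken before the endpoint is measured and is not split by group. It can therefore be met while one group is short of 31 week-12 pairs. The perinatal group is the natural concern: the protocol describes it as not previously studied, and its background section says these participants find regular follow-up difficult.

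**Working it through.** **Inputs, all from section 10.1.** Confidence level 95%; probability of achieving the width 0.90. Cell-mediated endpoint: SD 3.4, full width 3. Antibody endpoint: SD 0.7, full width 0.6. Both are on the natural log scale.

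**Formula.** This is the calculation behind the cited Stata command. The required n is the smallest n for which

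P(2 × t(0.975, n−1) × s / √n ≤ w) ≥ 0.90, where (n−1)s²/SD² follows a chi-square distribution with n−1 degrees of freedom.

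**Reproducing the plan's figures.**

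- Cell-mediated: n = 29 gives 0.895 and n = 30 gives 0.924, so 30 is confirmed.
- Antibody: n = 30 gives 0.882 and n = 31 gives 0.912, so 31 is confirmed.

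**Total.** Every participant supplies both endpoints, so each group needs max(30, 31) = 31, and two groups need 2 × 31 = 62. The most even split of 61 is 31 and 30. The group of 30 still meets the cell-mediated target (0.924) but misses the antibody target (0.882).

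**Effect of a smaller group on the antibody endpoint.** The 90%-assured width is 2 × t(0.975, n−1) × 0.7 × √(χ²(0.90, n−1)/(n−1)) / √n. At n = 30 this is 2 × 2.045 × 0.7 × √(39.09/29) / √30 = 0.607.

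| Pairs in the group | P(width ≤ 0.6) | 90%-assured width |
|---|---|---|
| 31 | 0.912 | 0.595 |
| 30 | 0.882 | 0.607 |
| 29 | 0.845 | 0.620 |
| 28 | 0.802 | 0.633 |
| 27 | 0.753 | 0.648 |

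**How a group could reach these sizes under section 6.7.** The protocol gives no attrition rate, so the losses and splits below are assumptions.

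- *Loss after dose 2.* If enrolment stops with 62 dosed twice, split evenly, a 5% loss leaves 31 × 0.95 = 29.5 pairs per group and a 10% loss leaves 31 × 0.90 = 27.9. The chance that both groups keep all 31 pairs is 0.98^62 = 0.29, 0.95^62 = 0.04 or 0.90^62 = 0.001 at losses of 2%, 5% or 10%.
- *Imbalance.* A 35/27 split at dose 2 satisfies the pooled count and leaves 27 in one group.

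**If all 70 are enrolled, 35 per group.** Reaching 31 in each group allows 4 losses per group (4/35 = 11.4%). With binomial losses, the chance that both groups reach 31 is 0.94, 0.53 or 0.14 at assumed total losses of 5%, 10% or 15%.

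**The case against.** The strongest reply has four parts.

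1. *The per-group target is already in the plan.* Section 10.1 requires the size in each population and recruits about 35 in each, and section 6.3 aims for 31 completers per group. Completion runs to week 48, normally a later milestone than week 12. This stands as a statement of intent. However, section 6.3 is an aim that no rule enforces, and it contradicts 61.
2. *Recruiting 70 leaves room for loss.* A reader might infer from section 6.7 that the plan allows nothing for loss after dose 2. The documents do not support that. Section 10.1 recruits 70 to end with 61, which covers nine losses (12.9%) at any stage, and a 10% loss from 70 leaves 63. What remains is that sections 6.3, 6.7 and 7.1 make 70 an upper limit, and the section 6.7 rule can be met before it is reached.
3. *The numerical effect is modest.* At n = 30 the 90%-assured interval factor for the fold change is exp(0.607/2) = 1.355, against exp(0.3) = 1.350. At n = 27 the width at the planning SD is 0.554, still below 0.6. The antibody SD was rounded up, and no success threshold depends on the width. All of this stands, and it limits the severity.
4. *The 35/27 split is unfavourable.* Starting from 35 per group, it needs no loss in one group and eight (23%) in the other. The protocol also includes wide visit windows because of the attendance difficulty. The split shows what the rule permits; it is not a forecast.

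**Conclusion.** The inconsistency is established from the protocol alone. With separate analyses and 31 needed for antibody, the evaluable total is 62, and no split of 61 delivers the stated 90% in both groups. That part is worth one participant and about three percentage points in one group (0.912 to 0.882).

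The pooled dose-2 count in section 6.7 is the more consequential weakness, because it guarantees neither 31 per group nor 31 week-12 pairs. Its size depends on assumed losses or imbalance: 0.85, 0.80 or 0.75 at 29, 28 or 27 pairs. Full recruitment of 70 at about 35 per group would offset part of it.

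A reader might infer that 61 was obtained by adding the two endpoint sizes, 30 + 31. The sum matches, but the protocol does not say so, and 70 less about 13% (60.9) gives the same figure. The point does not depend on the origin. Nor do the documents support a claim that the trial's conclusions would fail: what is at risk is a stated precision in one group. Severity is moderate.

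**What to change.** - Synopsis and section 10.1: change 61 to 62 evaluable, stated as 31 per group.
- Section 6.7: count replacement separately in each group, and continue until 31 participants in that group have both baseline and week-12 samples collected, within the existing cap of 70. Count collected samples, not valid assay results: section 7.2 has processed samples batch shipped for analysis, so assay validity may not be known while enrolment is open.
- Sections 6.3, 6.7 and 10.1: use this one count in place of completion, second injections and an undefined evaluable number.
- If the cap is reached before a group has 31, report the precision achieved in that group.

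The cost is wording, tracking of week-12 samples by group, and possibly continued enrolment up to the cap. The cap does not rise, so the change improves the chance of 31 per group without guaranteeing it.
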